3.6 Randomization

Subjects will be stratified by sex and then randomized equally to one of three groups (one beef patty, one Impossible Burger, or two Impossible Burgers).

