7.0 Data Analysis

7.1 Statistical Analysis plan

The post-prandial change in net protein balance (i.e., protein synthesis minus protein breakdown) relative to the baseline in each group will be the primary outcome. Responses of the rates of protein synthesis and breakdown will be secondary outcomes. Additional secondary endpoints will be muscle protein synthesis, plasma EAA and insulin area under the curve above baseline values, and protein kinetics normalized by caloric and EAA intake. Correlation analysis of the relation between protein kinetics and the EAA content of the protein food source will be additional secondary endpoints.

One-way ANCOVA will be used to compare differences in protein kinetics (FSR, NB, PS, and PB) and protein kinetics normalized by caloric and EAA intake. Plasma EAAs and insulin area

under the curve above fasting values will be assessed by a one-way ANOVA. All significant main effects of group will be followed with Bonferroni-adjusted pairwise comparisons. Partial Pearson's correlation coefficients controlling for protein source (beef patty or Impossible Burger) will be used for the correlation analysis. Statistical significance will be accepted at $p < 0.05$.

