7.2 Sample Size Calculation & Power Analysis

A group size of 8 per group was a priori determined based upon an ANCOVA model to compare the protein sources and amounts with respect to mean response of net protein synthesis after adjusting for baseline measures. With this sample size, the ANCOVA model has 80% power to detect effect sizes of $f = 0.484$ or larger. This estimate assumes that the baseline covariate explains 50% of the variation in the response. A 5% α -level will be used to determine statistical significance.

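### Plasma EAA and insulin areas are tested by ANOVA on a fasting-subtracted value, which fixes the baseline slope at 1; adding the fasting level as a covariate may improve precision on these secondary endpoints at small cost

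*Combined protocol and SAP*

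**What the plan says.** Section 7.1 lists "plasma EAA and insulin area under the curve above baseline values" among the secondary endpoints. It then says that area "under the curve above fasting values will be assessed by a one-way ANOVA". No covariate is mentioned.

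The sentence before it treats the other endpoints differently: "One-way ANCOVA will be used to compare differences in protein kinetics (FSR, NB, PS, and PB"). Section 7.1 does not name the covariate. Section 7.2 supplies it when it describes the model as comparing "mean response of net protein synthesis after adjusting for baseline measures", with baseline assumed to explain half of the variation. The plan gives no reason for handling the plasma endpoints another way.

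Both hypotheses in section 2.0 include greater rises in plasma EAA as part of the anabolic response. Section 3.1 lists blood draws at 0, 120, 150, 180, 210 and 240 min and then every 30 min to 600 min. The plan does not say which pre-meal sample or average is the fasting value, or whether area below fasting counts as negative or is dropped.

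**The concern.** Subtracting the fasting level assumes that a participant who starts one unit higher stays exactly one unit higher on average through the six post-meal hours. If the true slope differs from 1, the subtraction leaves baseline-related variance in the endpoint, and an ANOVA without a covariate cannot remove it. With 8 per arm and Bonferroni-adjusted pairwise tests, that could widen the intervals for the plasma EAA part of both hypotheses.

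The result also depends on a fasting value that the plan leaves undefined. Both matters can be settled now with data the trial already plans to collect and a method it already uses for the kinetic endpoints.

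**Working it through.** **Inputs from the plan.** Three groups of 8, N = 24 (4.0, 7.2); equal allocation stratified by sex (3.6); post-meal window 240 to 600 min, i.e. 360 min (3.1); f = 0.484, power 80%, baseline R² = 0.50, alpha 5% (7.2).

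**Assumed, because the documents give no values for EAA or insulin.** r is the correlation between the fasting level and the mean post-meal level. s is the fasting SD divided by the post-meal SD. The true slope is r/s.

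**1. The plan's own figure.** Section 7.2 says "the ANCOVA model has 80% power to detect effect sizes of $f = 0.484$ or larger". The noncentrality is λ = N f²/(1 − R²) = 24 × 0.484²/0.50 = 11.24. With 2 and 20 df, power is 80.0%, and the smallest f giving 80% is 0.4838. The figure reproduces. R² = 0.50 corresponds to r = 0.707, but the plan states it for net protein synthesis, not for plasma concentrations.

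**2. Algebra.** Let M be the mean post-meal concentration and C the fasting value. Net area = 360 × (M − C). An ANOVA on it is an ANCOVA of M on group and C with the slope fixed at 1. If C is then added as a covariate, total area (360M) and net area (360M − 360C) differ only by a multiple of C. The C coefficient shifts, and the group contrasts and residuals are identical. The endpoint can therefore stay as defined. This holds only for net area, not if area below fasting is dropped.

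**3. Variances, with post-meal variance set to 1.**
- Subtraction and ANOVA (21 df): 1 + s² − 2rs.
- ANCOVA (20 df): 1 − r², times 1 + 1/(24 − 3 − 2) = 1.053 for chance covariate imbalance.

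With s = 1 the ratio before the penalty is (1 + r)/2:

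| r | before penalty | after × 1.053 | net change in variance |
|---|---|---|---|
| 0.3 | 0.65 | 0.68 | 32% lower |
| 0.5 | 0.75 | 0.79 | 21% lower |
| 0.7 | 0.85 | 0.895 | about 10% lower |
| 0.9 | 0.95 | 1.00 | none |
| 0.95 | 0.975 | 1.03 | 3% higher |

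With s = 0.5 the ratios after the penalty are 1.01 (r = 0.3, slope 0.6), 1.05 (r = 0.5, slope 1), 0.97 (r = 0.71, slope 1.41) and 0.84 (r = 0.8, slope 1.6). Here ANCOVA is slightly worse for slopes of about 0.56 to 1.34.

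**4. Illustration in power terms.** Suppose EAA had r² = 0.50 and equal SDs. Residual variance is 2 × (1 − 0.707) = 0.586 by subtraction and 0.500 by ANCOVA. At f = 0.484, λ = 24 × 0.484²/0.586 = 9.6 on 2 and 21 df gives 73%, against 80% for ANCOVA. Simulation (10,000 trials) gives 73% and 78%; the formula for ANCOVA leaves out chance imbalance.

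**5. EAA simulation** (3,000 trials, 8 per arm; assumed fasting 900 µM, SD 120, sample noise 50). SE of beef minus one burger in µM·min, using the same five-sample fasting mean in both analyses:

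| r | subtraction | ANCOVA | change in SE |
|---|---|---|---|
| 0.5 | 23,521 | 21,138 | 10% lower |
| 0.7 | 19,472 | 18,803 | 3% lower |
| 0.9 | 14,054 | 14,113 | none (0.4% higher) |
| 1.0 | 10,701 | 11,062 | 3% higher |

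**6. Downside when the true slope is 1.** By formula, variance is 5% higher and intervals are √1.053 × 2.086/2.080 = 1.029 times as wide. By simulation, (11,062/10,701)² = 1.069, or 7% more variance. The power loss is about 2 points (simulated 80% to 78%).

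**The case against.** The strongest reply is that nothing here is invalid. Section 3.6 says "Subjects will be stratified by sex and then randomized equally to one of three groups", so an ANOVA on a baseline-subtracted area gives an unbiased comparison with the intended type I error. Baseline is already taken into account by the subtraction, and the endpoints are secondary. All of that stands.

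It also stands that the gain cannot be sized from the documents. A reader might infer that ANCOVA is always at least as precise. That is exact only for residual variance before the small-sample cost; with 24 completers ANCOVA loses a few percent when the slope is near 1.

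A reader might also claim a larger gain by comparing ANCOVA on a five-sample mean with subtraction of one fasting reading: 15%, 11% and 12% in SE at r = 0.5, 0.7 and 0.9. That mixes two changes. At r = 0.9 averaging alone takes the SE from 16,008 to 14,054, and ANCOVA adds nothing. The plan nowhere says that a single reading is used.

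Nor does multiplying the fasting value by 360 min amplify its noise relative to the endpoint, since the post-meal area is on the same scale.

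Finally, the pre-meal window is not settled. The section 3.1 schedule has a supplement taken at 120 min and the study food served at 240 min, and the visit text places the food after the four-hour sample. Sections 5.1 and 7.3 do not say at which times EAA and insulin are assayed. The samples from 120 to 240 min cannot simply be called fasting until this is reconciled.

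**Conclusion.** The point holds as a minor precision issue on secondary endpoints. The plan fixes the slope on fasting concentration at 1 for plasma EAA and insulin, while the kinetic model is described as working "after adjusting for baseline measures".

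On assumed equal SDs, the net variance reduction from estimating the slope is about 21%, 10% and 0% at r = 0.5, 0.7 and 0.9. In the EAA simulation the like-for-like SE gain is about 10%, 3% and 0%. Against this stands about 5–7% more variance, or about 3% wider intervals, if the true slope is 1. These figures rest on assumed SDs, correlations and sample noise. Nothing is quantified for insulin.

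The documents do not support a claim of bias, of inflated type I error, or that the conclusion on either hypothesis would change. The primary outcome is untouched. The case for the change is that the likely loss is small and bounded, the possible gain is larger, and the fasting value has to be defined in any event.

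**What to change.** In section 7.1:

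1. Keep the endpoint as area above baseline, and state that it is net area over the post-meal window with negative parts included.
2. Replace the ANOVA for plasma EAA and insulin with: *one-way ANCOVA with the mean fasting concentration as covariate*. Use the same fasting value in the subtraction and as the covariate. Total area then gives the same group contrast, so no change of endpoint is needed.
3. Define the fasting value as the mean of the assayed pre-meal samples, and list their times. First reconcile the 120 min supplement entry in the section 3.1 schedule with the food served at 240 min.
4. State the analysis scale for insulin before the data are seen, since the figures above do not cover it.

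The cost is a few lines in section 7.1 and a clarified schedule in section 3.1. Statistically it is one of 21 residual degrees of freedom, with the worst case given above. No extra blood draws are needed.

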1.0 Background and Rationale

1.1 Introduction:

According to the USDA Economic Research Service Food Availability Data, beef consumption has been on a general decline for the past 40 years, with current per capita consumption approximately 35% lower in 2020 than in 1980. Some of this decline over the past few years can be attributed to politically motivated claims that carbon emissions from cattle represent a major threat to the global environment. However, the major reason for declining beef consumption is the widely promulgated claim that beef is unhealthy. The hamburger in particular has become a poster child for the notion that beef consumption is responsible for the increasing occurrence of obesity in the United States. The trend of decreasing beef consumption due to perceived health concerns, particularly obesity and associated health problems, has led major fast-food chains such as Burger King and McDonalds, to offer vegetarian burgers as healthy alternatives to the traditional beef burger. However, examination

of the components of the macronutrient matrix of a typical vegetarian burger gives reason to question the health benefits as compared to a traditional beef patty-hamburger.

1.2 Previous research on the topic:

[figure not shown]
One of the principal nutritional benefits of dietary protein in a food source is the stimulation of muscle protein turnover and the net gain of body protein (the anabolic response) (1).

Table 1 shows key aspects of the macronutrient matrix of the Impossible Burger and an 80/20 percent beef patty, with particular emphasis on the protein/essential amino acid (EAA) content.

Table 1. Proposed Experimental Groups			
	80/20 Beef Patty	Impossible Burger	2 Impossible Burgers
Amount (oz)	4 oz	4 oz	8 oz
Protein (g)	19 g	19 g	38 g
EAA (g)	8.9 g	4.2 g	8.4 g
Calories	287	240	480
Calories / g EAA	32	57	57

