The Impossible Burger was chosen as a representative vegetarian burger because soy, which is the highest quality plant-based protein, is the principal protein source (2). Four-ounce servings of a beef patty and of an Impossible Burger each provide 19 g of protein. However, a closer inspection of the macronutrient matrix of the two food sources reveals that the 4 oz beef patty contains more than twice the amount of essential amino acids (EAAs) as compared to a 4 oz Impossible Burger. We recently completed an NCBA-supported study in which the anabolic responses to seven different “ounce equivalents” of protein food sources, as described by the USDA My Plate, were quantified using stable isotope tracers. Rather than being metabolically equivalent, as implied by their designation by My Plate as “ounce equivalent” protein food sources, we found that there was a linear relation between the net gain in body protein and the EAA content of the protein food source (**Figure 1A**) (3). Moreover, the slope of the relation between EAA content and increase in net protein balance was approximately 1, meaning that any difference in EAA content directly corresponded to an equivalent difference in net body protein gain (**Figure 1B**).

These results support the notion that the EAA content of a protein food source is principally responsible for the magnitude of the anabolic response. This fundamental concept is the basis for the scoring of protein quality by the Digestible Indispensable Amino Acid Score (DIAAS) (4). With relevance to the comparison of a beef patty and an Impossible Burger, we found that consumption of 2 ounces of beef resulted in an anabolic response that was approximately 4 g net gain of protein greater than the response to consumption of 2 ounces tofu (Figure 1) (3). The difference in anabolic responses corresponds to the difference in the EAA content of the two protein food sources (Figure 1A). Muscle protein fractional synthesis rate was also greater in those consuming beef as opposed to tofu. Further, compilation of our in-house data set across various populations and food sources indicates that the EAA content of a protein food source explains 80.4% of the variance in the total amount of body protein gained (5). This

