large dataset has allowed us to develop a predictive equation that indicates the total amount of body protein gained will be 7.6 g from 4.2 g of EAA (the Impossible Burger) and 16.5 g from 8.9 g of EAA (beef patty). Stated differently, the greater EAA content of a 4 oz beef patty is predicted to elicit more than double the anabolic response to the same amount of an Impossible Burger.

Plant-based burgers such as the Impossible Burger are being marketed as a one-for-one replacement for beef-based burgers, but the disregard for protein quality is misleading and creates a false perception of equivalent nutritional benefit of the two protein food sources. In

addition to the greater EAA content per gram protein, the profile of EAAs in beef protein more closely reflects the dietary requirements for individual EAAs, as reflected by a DIAAS approximately 40% greater than soy protein. In addition, the overall macronutrient matrix of a protein food source can potentially influence the anabolic response by affecting the temporal EAA response. Both the peak concentration of EAAs after consumption as well as the time to reach the peak concentration affect the anabolic response (5). The Impossible Burger contains various binders and starches that could potentially interfere with the absorption of the EAA from the protein matrix, with a resultant slowing of the rate of absorption and blunting of the maximal concentrations of EAAs in the blood and the speed at which the peak concentrations are reached. These factors likely have a corresponding negative impact on the magnitude of the anabolic response. Since no such issues impede the digestibility of beef protein, it is reasonable to propose that the plasma EAA levels will reach higher peak EAA concentrations, and achieve the peak concentrations more rapidly, than ingestion of the same amount of EAAs in the matrix of the Impossible Burger. As a result of both the advantageous profile of EAAs in beef protein and the more rapid absorption of EAAs, we propose that a beef patty will not only provide a greater anabolic response than an iso-nitrogenous amount of Impossible Burger, but that also consumption of 4 oz of beef patty will also elicit a greater anabolic response than consumption of two Impossible Burgers.

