3.1 Study Visits

Visit 1: subjects will come to the UAMS TRI for informed consent discussion. Once consent is obtained, subsequent study procedures will be performed. A medical history questionnaire including allergies and list of current medications will be completed. Females of child bearing capacity will be asked to provide a urine sample for pregnancy testing. About 4mL of venous blood will be drawn to send for complete blood count for study criteria. Blood and urine samples will be sent to LabCorp.

Subjects will be asked to perform the following tests and measurements at visit 1:

Standing height without shoes (in cm),

Body weight without shoes (in kg),

If subject meets the requirements (fasted for at least 8 hours, caffeine-free for at least 12 hours, and did not perform strenuous exercise during the past 24 hours) to perform the DEXA scan and In Body scan on visit 1, these tests will be performed at that time. If they do not, these tests will be performed at Visit 2.

Run-in meals will be discussed with subjects to elicit food allergies or intolerances.

Visit 2: Subjects return to the UAMS TRI. If they will undergo the DEXA and InBody scans, the must have fasted for at least 8 hours, avoided caffeine for at least 12 hours, and avoided strenuous exercise during the past 24 hours. They will be asked about any adverse events since last visit. The In Body, DEXA, ultrasound scans will be performed if these were not done at visit 1. Two days' of run-in meals will be dispensed with instructions on their preparation. Meals will be consumed for the two days immediately preceding Visit 3.

Visit 3: Subjects return to the UAMS TRI having fasted overnight. Study staff will ask about adverse events since their last visit. Vital signs (heartrate, blood pressure and oral temperature) will be measured. The study nurse will insert an IV catheter into a vein of one of the subjects' arms to use for periodic blood sampling, warming the arm by means of a heating pad or a heated plastic box. A second IV catheter will be placed into a vein on of the subject's other arm to use for stable isotope infusion.

After an initial blood sample is obtained, the priming dose of isotopes are given IV push, the constant infusions are begun, and a timer is started. Blood and muscle samples are obtained according to the schedule below.

The study food is served after the 4:00 blood/muscle sample are obtained. Subjects are asked to consume the study food within 10 minutes.

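### Secondary endpoint in 7.1: with one EAA value per arm, the source-controlled partial correlation is exactly a two-versus-one Impossible Burger contrast and cannot address EAA content as such or across foods

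*Combined protocol and SAP*

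**What the plan says.** Section 7.1 lists as an additional secondary endpoint the "Correlation analysis of the relation between protein kinetics and the EAA content of the protein food source". The method is a partial Pearson correlation: "correlation coefficients controlling for protein source (beef patty or Impossible Burger) will be used for the correlation analysis". Significance is at p < 0.05. No other control variable is named for it.

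The EAA values are in Section 1.2 ("Table 1. Proposed Experimental Groups"), one per arm, with no subject-level EAA dose described anywhere.

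For the group comparison of protein kinetics, 7.1 plans a one-way ANCOVA, and "All significant main effects of group will be followed with Bonferroni-adjusted pairwise comparisons". Section 7.2 describes that ANCOVA as adjusted for baseline: "This estimate assumes that the baseline covariate explains 50% of the variation in the response".

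The background in 1.2 reports that in an earlier study of several protein foods "there was a linear relation between the net gain in body protein and the EAA content of the protein food source". The plan does not say that the correlation endpoint is meant to confirm that relation, but the wording is close.

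**The concern.** The beef arm has a single EAA value. A two-level source variable plus EAA content therefore fits the three arm means perfectly, and controlling for source removes everything that beef could say about EAA. What is left is 4.2 g against 8.4 g within the Impossible Burger, where protein, calories and weight double too.

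A significant result would be reported under an endpoint named for EAA content and could be read as support for it. Yet it would come out the same whether or not beef lies on the EAA line. The 4.7 g EAA gap between beef and one burger, for which 1.2 predicts gains of 16.5 g and 7.6 g of body protein, plays no part. The result would also concern the same difference as the planned one-versus-two pairwise comparison, so reporting both as separate evidence would count one difference twice.

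**Working it through.** **The plan's own figure.** The documents give no power for the correlation. The nearby ANCOVA figure reproduces: noncentrality 24 × 0.484² / (1 − 0.5) = 11.24 on 2 and 20 df gives 80.03% power against the stated 80%. Nothing below disputes it.

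**Inputs (Table 1; group size from 4.0), full consumption assumed.**

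| | Beef | One Impossible Burger | Two Impossible Burgers |
|---|---|---|---|
| EAA (g) | 8.9 | 4.2 | 8.4 |
| Protein (g) | 19 | 19 | 38 |
| Calories | 287 | 240 | 480 |
| Ounces | 4 | 4 | 8 |
| Completers | 8 | 8 | 8 |

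**Step 1: remove source from EAA.** Beef: 8.9 − 8.9 = 0. The Impossible Burger mean is (4.2 + 8.4)/2 = 6.3, so the residuals are −2.1 and +2.1.

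**Step 2: the partial r.** Let D be the two-burger mean minus the one-burger mean, SSW the within-arm sum of squares over all three arms, and s² = SSW/21.
- Cross-product of residuals: 2.1 × 8 × D = 16.8 D.
- EAA residual sum of squares: 16 × 2.1² = 70.56, with root 8.4.
- Outcome residual sum of squares about the source means: SSW + 4D².
- So r = 16.8 D / (8.4 √(SSW + 4D²)) = 2D / √(SSW + 4D²).
- Then t = r √(21/(1 − r²)) = 2D/s = D / (s √(2/8)).

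This is the two-versus-one contrast with three-arm pooled error. The 2.1 cancels. Beef subjects enter only through s.

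**Step 3: replace EAA.** The residuals become ±9.5 g for protein, ±120 for calories and ±2 for ounces. All are proportional to ±2.1, so r is unchanged. Across all three arms EAA correlates only 0.41 with protein or ounces and 0.57 with calories; after source control every one of these correlations is 1.00.

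**Step 4: threshold.** The two-sided 5% critical t on 21 df is 2.080. Critical |r| = 2.080/√(2.080² + 21) = 0.413, and D/s = 2.080 × 0.5 = 1.04.

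**Numerical check.** Over 2,000 simulated trials the largest gap between the two t statistics was 1.2 × 10⁻¹⁴. In one data set r = 0.6734 (t = 4.174) for EAA, protein, calories and ounces alike. It stayed at 0.6734 when all beef responses were lowered by 8.9 g or raised by 100 g. The correlation without source control fell from 0.757 to 0.352 when beef was lowered by 8.9 g.

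**What each correlation can tell apart.** Three scenarios for mean protein gain (beef / one burger / two burgers, g), with normal outcomes, equal SDs and assumed SDs of 4, 6, 8 and 12 g, because the documents give none. The 15.6 in scenario A lies on the line through the two values predicted in 1.2: slope 8.9/4.7 = 1.89, and 7.6 + 1.89 × 4.2 = 15.6 after rounding to one decimal.

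| Scenario | Partial r: mean | Partial r: significant | No source control: mean r | No source control: significant |
|---|---|---|---|---|
| A, EAA-driven: 16.5 / 7.6 / 15.6 | 0.65, 0.49, 0.39, 0.27 | 97, 71, 47, 24% | 0.72, 0.56, 0.45, 0.32 | (a true EAA effect) |
| B, protein amount only: 7.6 / 7.6 / 15.6 | 0.65, 0.49, 0.39, 0.27 | 97, 71, 47, 25% | 0.29, 0.22, 0.18, 0.13 | about 22% down to 8% |
| C, source only: 16.5 / 7.6 / 7.6 | about 0 | about 5% | 0.42, 0.34, 0.28, 0.20 | about 59% down to 14% |

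The partial r cannot tell A from B. The correlation without source control differs between them, but it is often significant under C, where EAA has no effect.

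**Overlap with the ANCOVA contrast.** Under the null at the plan's R² of 0.5, the partial-r t and the baseline-adjusted one-versus-two t correlate about 0.7 if post-prandial values are correlated. For change scores the figure is about 0.9 (equal pre and post SDs assumed). If baseline is also controlled in the correlation, the two t statistics are equal (2.945 and 2.945 in one data set).

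**The case against.** **Controlling for source is defensible.** Section 1.2 itself gives reasons other than grams of EAA why beef and the Impossible Burger might differ: amino acid profile, binders and starches, and speed of absorption. Source is a plausible confounder, and scenario C shows the control doing its job: the partial r stays at 5% while the uncontrolled correlation is significant in about 14–59% of runs. This stands. A reader might infer that source control is simply a mistake and that dropping it yields the right EAA test; the documents do not support that. With one beef level, neither version isolates EAA.

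**The partial r might be taken for a plain repeat of the ANCOVA comparison, or for an analysis that ignores baseline.** Neither follows. The target difference is the same, but the ANCOVA adjusts for baseline and its pairwise tests are Bonferroni-adjusted after a significant main effect. The primary outcome is a change from baseline, and 7.1 does not say whether the correlation uses change or post-prandial values. What can be said is that no baseline covariate is named and the scale is open.

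**Intake may vary between subjects.** Section 3.1 says only that "Subjects are asked to consume the study food within 10 minutes". If each subject ate a uniform 80–100% (an assumption), beef would carry about 3% of the EAA residual sum of squares, so little changes.

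**It is one secondary endpoint, and the harm lies in interpretation.** True, and it limits the weight of the point. It does not remove it, because a p-value would be attached to a question that the statistic cannot answer.

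**Conclusion.** The point holds as an exact identity, given one fixed EAA value per arm and full consumption. The source-controlled partial r measures the effect of two Impossible Burgers against one. It cannot speak to EAA as distinct from protein, calories or amount eaten, nor to a relation across foods. If EAA content were instead expressed per gram of protein, both Impossible Burger arms would share one value (4.2/19 = 8.4/38) and the partial correlation would be undefined.

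The SD-based percentages rest on assumed SDs of 4–12 g and normal outcomes; the identity does not.

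A reader might infer that the trial's main conclusions are at risk. They are not: the primary outcome, the sample size and both hypotheses are unaffected, and hypothesis 1 tests beef against one burger directly through the ANCOVA. The point should be fixed in the analysis plan, as a matter of what this endpoint may claim.

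**What to change.** In 7.1:

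1. Label the source-controlled partial r as an Impossible Burger dose (amount) contrast.
2. State that it is not evidence separate from the one-versus-two pairwise comparison, and that no EAA-specific or cross-food conclusion will be drawn from it.
3. State whether post-prandial or change-from-baseline kinetics are correlated, and whether baseline is also controlled.
4. If the correlation without source control is reported alongside, label it descriptive, with no significance claim. It uses all three arms but confounds EAA with source, and it can be significant with no EAA effect: about 8–22% of runs if protein amount alone drives the response, about 14–59% if source alone does.

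The cost is a few sentences and, if item 4 is taken up, one extra correlation per kinetic outcome. No new subjects or data are needed. The downside is that the endpoint gives up its EAA-specific inferential claim, which this three-arm design cannot support by either correlation.
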